6. INTRODUCTION

Nonalcoholic fatty liver disease (NAFLD) is one of the most common causes of chronic liver disease in the world today. Nonalcoholic steatohepatitis (NASH), which is the more advanced form of NAFLD, is defined as the presence of hepatic steatosis and inflammation with hepatocyte injury (ballooning), with or without fibrosis.¹ NASH is associated with increased mortality rates due to cardiovascular-, liver-, and cancer-related deaths.

Currently, there are no approved drugs for the treatment of NASH. With the increasing prevalence of obesity and obesity-related diseases, NASH could soon become the leading indication for liver transplantation and the leading cause of hepatocellular carcinoma (HCC).² There is an urgent need to develop safe and effective therapies for NASH.³

Fibroblast growth factor 21 (FGF21) is a nonmitogenic hormone that is an important regulator of energy metabolism.⁴ FGF21 is a member of a hormone-like subgroup within the fibroblast growth factor (FGF) superfamily. Like other members of this subfamily (i.e., FGF19 and FGF23), FGF21 has low binding affinity for heparin, which allows for transport into the circulation and subsequent action at distant sites. High-affinity binding of FGF21 to FGF receptors (FGF-Rs) occurs only in the presence of the FGF-R co-receptor, β -Klotho; the restricted expression pattern of β -Klotho defines the target tissues for FGF21 activity. FGF-Rs and β -Klotho are co-localized in liver, pancreas and adipose tissue, which are responsible for glucose and fat metabolism.⁵ Notably, in contrast to FGF19, FGF21 does not signal through FGF-R4/ β -Klotho⁶ and, therefore, is not mitogenic, nor does it regulate bile acid metabolism.

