8.3.1 Inclusion Criteria

1. Signed written informed consent
 - a) Participants must be willing to participate in the study and sign the informed consent form(s) (ICF[s])
 - b) Participants (and caregivers as applicable) must be willing and able to complete all study-specific procedures and visits
2. Liver biopsy performed within 6 months (26 weeks) prior to the Screening Period. Biopsy performed prior to ICF must be available to the central reader prior to randomization. If historical biopsy is not available, a liver biopsy will be performed during the Screening Period (see Section [8.5.1.1](#)). Biopsy must be consistent with NASH and cirrhosis according to the NASH CRN classification, as assessed by the central reader.
3. Participants taking anti-diabetic, anti-obesity, or anti-dyslipidemic medications must have been on stable regimens for at least 3 months (12 weeks) (6 weeks for statins) prior to and during the Screening Period. The investigator may contact the medical monitor regarding the stability of a participant's regimen when determining eligibility for study participation. Participants taking vitamin E at doses ≥ 800 IU/day must have been on stable doses for at least 6 months (26 weeks) prior to and during the Screening Period. Vitamin E treatment (≥ 800 IU/day) must not have been initiated after the qualifying liver biopsy was performed.
4. Age and reproductive status
 - a) Men or women 18 to 75 (inclusive) years of age
 - b) Women of childbearing potential (WOCBP) must have a negative pregnancy test (minimum sensitivity 25 IU/L or equivalent units of human chorionic gonadotropin) within 24 hours prior to the start of study medication
 - c) Women must not be breastfeeding at any time during the study

- d) WOCBPs must agree to follow instructions for method(s) of contraception for the duration of treatment (BMS-986036 or placebo) plus 5 half-lives of study medication (5 days) plus 30 days (duration of ovulatory cycle) for a total of 35 days after the end of the Double-Blind Treatment Period
- e) WOCBPs who are continuously not heterosexually active are exempt from contraceptive requirements but must undergo pregnancy testing as described in the Schedule of Activities in Section 1

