For associated primary and secondary endpoints, the NASH CRN system²⁷ will be used to score the histologic samples and results are reported as the NAFLD Activity Score (NAS) and the NASH CRN Fibrosis Score. The NASH CRN system is based on the concept that necroinflammatory lesions and stage of fibrosis should be evaluated separately; it assesses liver biopsies for degree of steatosis (0-3), lobular inflammation (0-3), hepatocellular ballooning (0-2), and fibrosis (0-4).

NAS

The 3 categories of steatosis, lobular inflammation, and ballooning scores are added together in an unweighted fashion to determine the NAS, which ranges from 0 to 8 (see Table 7 below).

The NAS should not be considered a replacement for the Central Pathologist's diagnosis of NASH.

Table 7 NAS Scoring System

Histology Variable	Grade	Score
Steatosis	< 5%	0
	5% - 33%	1
	> 33% - 66%	2
	> 66%	3
Lobular Inflammation ^a	none	0
	< 2	1
	2 - 4	2
	> 4	3
Ballooning	none	0
	few	1
	many	2

NAS = NAFLD Activity Score

^a Foci per x200 field

Fibrosis

NASH CRN Fibrosis

Fibrosis is staged separately from NAS on a 0-4 scale: 0 (none); 1 (perisinusoidal or periportal fibrosis); 2 (perisinusoidal and portal/periportal fibrosis); 3 (bridging fibrosis); 4 (cirrhosis).

Ishak

A modified Ishak scoring system will also be used to stage fibrosis in the histologic samples. The Ishak system (0-6 scale) was originally developed to grade portal-based liver fibrosis

associated with viral hepatitis.²⁸ The modified Ishak system has been adapted to stage central-based liver fibrosis associated with NASH, and it also uses a 0-6 scale:

- 0: No fibrosis
- 1: centrilobular pericellular fibrosis
- 2: centrilobular and periportal fibrosis
- 3: bridging fibrosis (few bridges)
- 4: bridging fibrosis (many bridges)
- 5: early or incomplete cirrhosis
- 6: established or advanced cirrhosis

Morphometric Analysis of CPA and Fat Percentage in Stained Tissue

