9.4.1.2 Secondary Efficacy Endpoints

Secondary efficacy endpoints are as follows:

- Proportion of participants with Ishak Score improvement at Week 48
- Proportion of participants who achieve a ≥ 1 -stage improvement (as defined by NASH CRN Fibrosis Score) in fibrosis without worsening of NASH or NASH improvement (reduction of NAFLD Activity Score by ≥ 2 points with contribution from > 1 NAS component) at Week 48 as determined by liver biopsy
- Proportion of participants who achieve a ≥ 1 -stage improvement (as defined by NASH CRN Fibrosis Score) in fibrosis
- Proportion of participants with a decrease in CPA at Week 48
- Proportion of participants with NASH resolution (NAS component of ballooning = 0 and inflammation = 0-1) at Week 48
- Proportion of participants with NASH improvement (reduction of NAFLD Activity Score by ≥ 2 points with contribution from > 1 NAS component) at Week 48

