### 4.2 Secondary Efficacy Endpoints

The secondary efficacy endpoints are the proportion of participants with the following:

- Ishak Score  $>=1$  stage improvement at Week 48
- NASH CRN Fibrosis Score  $\geq 1$ -stage improvement (as defined by NASH CRN Fibrosis Score) in fibrosis without worsening of NASH or NASH improvement (reduction of NAS by  $\geq 2$  points with contribution from  $> 1$  NAS component) at Week 48
- $>= 1$ -stage improvement (as defined by NASH CRN Fibrosis Score) in fibrosis
- Any CPA decrease at Week 48
- NASH resolution (NAS component of ballooning = 0 and inflammation = 0-1) at Week 48
- NASH improvement (reduction of NAS by  $\geq 2$  points with contribution from  $> 1$  NAS component) at Week 48

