## 6.4 Exploratory Analyses

Analyses for exploratory endpoints (including biomarkers) will be performed using the mITT or safety populations. Categorical and continuous data will be summarized descriptively as presented in SAP [Section 6.5](#).

Exploratory dichotomous response variables will be summarized in a manner similar to that used for the primary and secondary efficacy analyses:

- Assessment of NASH CRN Fibrosis Score at Week 48
  - Proportion of participants with  $\geq 1$  stage improvement
  - Proportion of participants with  $\geq 2$  stage improvement
  - Proportion of participants with  $\geq 2$  stage improvement without worsening of NASH
  - Proportion of participants with NASH resolution
  - Proportion of participants with NASH improvement
- Assessment of Ishak Fibrosis Score at Week 48
  - Proportion of participants with  $\geq 1$  stage improvement
  - Proportion of participants with  $\geq 2$  stage improvement
- Assessment of CPA at Week 48
  - Proportion of participants with any improvement
- Hepatic fat fraction as measured using MRI-PDFF at Week 24 and Week 48
  - Proportion of subjects with  $\geq 30\%$  relative reduction,  $\geq 20\%$  relative reduction,  $\geq 10\%$  relative reduction, and  $\geq 5\%$  absolute reduction
- Liver stiffness as determined by MRE at Week 24 and Week 48
  - Proportion of subjects with  $\geq 19\%$  reduction
  - Proportion of subjects with  $\geq 15\%$  reduction
- Fibroscan elastography results at Week 48
  - Proportion of subjects with any improvement

In addition, summaries of  $\geq 1$  stage improvement, no change, and worsening will be tabulated and graphically presented for NASH CRN Fibrosis Score, Ishak Fibrosis Score, and NAS Total at Week 48. Participants without a Week 48 (or ET result) will be classified into the "Worse" category for these exploratory summaries.

Similarly to the primary and secondary efficacy endpoints, for exploratory endpoints based off the liver biopsy, the Week 48 result or ET biopsy will be used for Week 48 derivations. Participants without a Week 48 or ET biopsy will be classified as non-responders for liver biopsy endpoints at Week 48. Early termination visits for non-biopsy endpoints such as imaging and biomarkers may occur at other time points and will not

Sponsor: Bristol-Myers Squibb

Protocol No.: MB130-069

be summarized together with Week 48. For non-biopsy endpoints, ET will be summarized separately in the summary tables.

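### NASH resolution is scored on the Week 48 biopsy alone, so a participant who already met the rule at entry and stayed there would count as a responder

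*SAP*

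**What the plan says.** Protocol 9.4.1.2 lists the endpoint as "Proportion of participants with NASH resolution (NAS component of ballooning = 0 and inflammation = 0-1) at Week 48". SAP 4.2 carries the same definition: "NASH resolution (NAS component of ballooning = 0 and inflammation = 0-1) at Week 48". Both conditions concern the Week 48 biopsy. The other secondary endpoints in that list are changes from baseline: stage improvement, a fall in collagen area, or "NASH improvement (reduction of NAS by" at least 2 points. Resolution alone can be scored without looking at the baseline biopsy.

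SAP 6.1.2 analyses every secondary endpoint in the mITT population by the primary method, a one-sided Cochran-Armitage trend test at 0.05. SAP 5.0 defines mITT as randomised and dosed at least once, with no histological condition.

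On entry, Protocol 8.3.1 says: "Biopsy must be consistent with NASH and cirrhosis according to the NASH CRN classification, as assessed by the central reader". Protocol 8.5.1.1 adds that "The NAS should not be considered a replacement for the Central Pathologist's diagnosis of NASH".

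**The concern.** Resolution should mean that the lesion was present and is now absent. Under the rule as written, someone with ballooning 0 and inflammation 0 or 1 at entry needs only to stay there to be a success. Such participants carry no information about treatment-induced resolution, yet they add responders to all four arms. The reported rates would be too high, and the difference between active and placebo would shrink. A reader of the results could not tell resolved disease from disease that never met the threshold.

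**Working it through.** **Is a baseline condition supplied elsewhere?**

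- SAP 6.4 relists "Proportion of participants with NASH resolution" with no added condition.
- SAP 8.6 (biopsy scoring) defines the component grades but no responder rule.
- SAP 6.1.1.1 puts the baseline NASH score into a logistic sensitivity model for the primary endpoint. A covariate does not alter who is a responder.
- SAP 4.5 plans shift tables for each NAS component separately. They do not cross ballooning with inflammation, so they do not directly show how many met the joint rule at baseline.

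**Is a baseline that meets the rule ruled out at entry?** Inclusion criterion 2 in Protocol 8.3.1 rests on the central reader's diagnosis and sets no component minimum. Protocol 8.5.1.1 keeps diagnosis and score apart. The Introduction says NASH "is defined as the presence of hepatic steatosis and inflammation with hepatocyte injury (ballooning), with or without fibrosis", which points to ballooning being present at entry, but neither the visible criteria nor the endpoint definition turns this into a score.

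**The plan's own power figure.** Protocol 9.1 states at least 70% for the primary endpoint: rates 15/20/30/40%, 25 per arm, one-sided 0.05. No figure is given for resolution. With scores 0, 1, 2, 3 (centred: -1.5, -0.5, 0.5, 1.5), power = Φ[(d - 1.645 × s0)/s1], where

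- d = n Σ p(s - s̄) = 25 × 0.425 = 10.625
- s0 = √[p̄(1 - p̄) × n × Σ(s - s̄)²] = √(0.2625 × 0.7375 × 25 × 5) = 4.919
- s1 = √[n Σ p(1 - p)(s - s̄)²] = √(25 × 0.9194) = 4.794

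This gives Φ(0.528) = 70.1%, which reproduces the stated figure. At 38 per arm (Protocol 6.2) the result is 85.2%.

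**Illustration for resolution.** Inputs:

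- 38 per arm, from Protocol 6.2.
- At-risk resolution rates of 15/20/30/40%, an assumption borrowed from the primary endpoint.
- Share q meeting the rule at baseline, an assumption.
- Persistence to Week 48 of 80% in every arm, an assumption.

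Three versions are compared:

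- As written: observed rate = (1 - q)p + 0.8q, n = 38.
- At-risk denominator: rate p, n = 38(1 - q).
- mITT with baseline-met participants as non-responders: rate (1 - q)p, n = 38.

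For q = 10%, d is the same in all three, 38 × 0.9 × 0.425 = 14.535, because a constant added to every arm cancels in the trend. Only the noise differs.

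- As written, rates 21.5/26/35/44%: s0 = 6.410, s1 = 6.284, power Φ(0.635) = 73.7%.
- At-risk, n = 34.2: s0 = 5.754, s1 = 5.607, power Φ(0.904) = 81.7%.
- Non-responders: s0 = 5.855, s1 = 5.741, power Φ(0.854) = 80.4%.

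| q | Placebo / 40 mg as written | Difference (points) | Extra responders per 38 | Power as written | At-risk denominator | mITT, non-responders |
|---|---|---|---|---|---|---|
| 0 | 15.0 / 40.0% | 25.0 | 0 | 85.2% | 85.2% | 85.2% |
| 5% | 18.2 / 42.0% | 23.8 | 1.5 | 79.6% | 83.5% | 82.9% |
| 10% | 21.5 / 44.0% | 22.5 | 3.0 | 73.7% | 81.7% | 80.4% |
| 20% | 28.0 / 48.0% | 20.0 | 6.1 | 61.8% | 77.5% | 74.7% |

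The 20% row shows the far end; the Introduction's description of NASH makes it less plausible. Persistence matters little: at q = 10%, 70% persistence gives 74.4% as written and full persistence gives 72.5%.

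**The case against.** The strongest reply is that entry requires NASH, and the only description of NASH in the documents includes ballooning. On that reading a participant with ballooning 0 should hardly ever be enrolled. This stands as an argument about frequency. A reader might infer that the protocol permits such baselines; it does not say so. The supportable statement is that the visible criteria do not explicitly exclude them. Protocol 7 also cites a Section 8.3.3 that is not in the available text, and the Central Pathology Manual is not available, so a further criterion cannot be ruled out.

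A reader might also infer a larger loss. A two-arm comparison at 10% against 30%, with every baseline-met participant persisting, takes power from 71% to 62% at a 5% share and 54% at 10%. Those sums are right, but the planned analysis is a four-arm trend test, and full persistence is too strong when missing Week 48 biopsies count as non-response.

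Nor do the documents support a reading that the rule favours the drug. Baseline status precedes randomisation, so such participants are balanced in expectation and the contrast shrinks toward no effect. Chance imbalance remains: at a 10% share, the between-arm difference in that share has a 95% range of 1.96 × √(0.1 × 0.9 × 2/38), about ±13.5 points.

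Finally, the biopsy listings would let someone recover the baseline count. That is true, but it leaves the choice of denominator until after the results are seen.

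**Conclusion.** The gap in the definition is real and its effect is conditional. The rule has no baseline term, is applied to all mITT participants, and is not protected by an explicit score threshold in the visible entry criteria. Under the stated assumptions, the power lost relative to the at-risk analysis is 3.9 points (83.5 - 79.6) at a 5% baseline share and 8.0 points (81.7 - 73.7) at 10%. It is zero if no participant met the rule at entry. The share, the at-risk rates and the persistence are all assumed. This is a secondary endpoint in a Phase 2 study without multiplicity control, and the primary analysis is untouched. It merits correction because the correction is cheap, not because the damage is shown to be large.

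**What to change.** In SAP 4.2 and 6.1.2, and wherever SAP 6.4 reuses the endpoint, require that a NASH-resolution responder did not meet the definition at baseline, that is, had baseline ballooning ≥ 1 or inflammation ≥ 2. Choose one of two forms before unblinding:

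- keep the mITT denominator and count baseline-met participants as non-responders; or
- analyse only participants at risk at baseline.

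The first keeps the population in SAP 6.1.2; the second has slightly more power in the illustration. Show the protocol-defined result in all mITT participants as supportive, tabulate by arm how many met the rule at baseline, and record the change from Protocol 9.4.1.2 in SAP 2.5.

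The cost is a documented departure from the protocol wording and, if any such participants exist, a slightly smaller denominator or a lower response rate. The scores are already collected, so no new data are needed.

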### 4.3 Safety Endpoints

Safety will be assessed by the following as per the protocol specified schedule of assessments:

- Incidence and frequency of treatment-emergent AEs and SAEs
- ECGs at Week 24, and Week 48
- Vital signs at each visit
- Physical examinations at each visit through Week 52/PTFU
- Laboratory evaluations at each visit through Week 52/PTFU
- BMD as measured by DXA Week 48/ET, and 6 months (1 month is defined as 4 calendar weeks) after the Week 52/PTFU Visit
- Anti-BMS-986036 antibodies at each visit with follow-up for up to 14 months (1 month is defined as 4 calendar weeks) after the Week 52/PTFU Visit
- Anti-FGF21 antibodies at each visit with follow-up for up to 14 months (1 month is defined as 4 calendar weeks) after the Week 52/PTFU Visit

#### 4.3.1 Adverse Events

The definition of adverse events (AE) and serious adverse events (SAE) as well as their time periods for collection can be found in the [Protocol Section 8.5.3.1](#) and [Protocol Appendix 9](#).

Adverse event on special interest (AESI) will be programmatically determined by searching a predefined list of preferred terms for gastrointestinal events or bone-related events. Injection site reactions are determined via a checkbox in the eCRF. Additional details for injection site reactions will be collected including injection-site erythema and edema.

#### 4.3.2 Electrocardiograms (ECG)

- Absolute and change from baseline values
- Post-baseline abnormalities defined by the below categories:
  - Absolute QTcF (QT interval corrected using Fridericia's formula) prolongation

Sponsor: Bristol-Myers Squibb

Protocol No.: MB130-069

- >450 msec
- >480 msec
- >500 msec
- Change from baseline in QTcF Interval
  - >30 msec
  - >60 msec

#### 4.3.3 Vital Signs

- Absolute and change from baseline values

#### 4.3.4 Physical Examinations

Full or abbreviated physical examinations will be conducted at each visit through Week 52/PTFU.

#### 4.3.5 Clinical Laboratory Parameters

- Absolute and change from baseline values
- Potential hepatotoxicity by time point
  - Aspartate aminotransferase (AST) or alanine aminotransferase (ALT) > 3 x upper limit of normal (ULN) or > 5 x ULN
  - Total Bilirubin > 2 x ULN
  - (AST or ALT) > 3 x ULN and Total Bilirubin > 2 x ULN
- Postbaseline abnormalities defined by the below categories:
  - Serum albumin < 2.8 g/dL
  - Platelet count < 75 x 10^3/ μL
  - Fasting plasma glucose < 60 mg/dL or > 350 mg/dL
  - Fasting triglycerides > 500 mg/dL
  - Estimated glomerular filtration rate (eGFR) < 30 mL/min/1.73 m^2

